5.2.2 Male circumcision status

Circumcision status of males will be determined by participant self-report. Male participants will be shown illustrations on laminated cards of a circumcised and uncircumcised penis and given supportive instructions from the interviewer. Men will be asked to identify which of the illustrations they most resemble. See Appendix R.

5.2.3 Household

A household will be defined as a group of people who share a physical structure such as a compound or homestead and who consume or make some contribution to food and other shared household resources. Households will be eligible for participation in this study if they are within the predefined study area.

5.2.4 Household resident

A household resident is defined as an individual who:

1. has been sharing a physical structure such as a compound or homestead and who has been consuming or making some contribution to food and other

shared household resources; guests who stayed at the household the night before will also be offered participation (if they are 18-49 years of age) ; and

2. is listed by the head of household as being a household resident or overnight guest the prior night on the Household Composition Form(Appendix B)

5.2.5 Head of household

The head of household is defined as the person who is recognized within the household as being the head.

5.3 Participant Inclusion/Exclusion Criteria

5.3.1 Pre-cohort surveys

- Inclusion criteria
 - Resides in selected household
 - Reports age between 18-49 years
 - Agrees to study procedures
 - Able to provide answers to the pre-cohort survey questions administered in either English or siSwati
 - Able to provide consent in either English or siSwati

5.3.2 Short-term Longitudinal cohorts (Cohorts A1 and A2)

- Inclusion criteria
 - Meets eligibility criteria for pre-cohort survey (listed above)
 - Confirmed HIV-negative by Swazi rapid HIV test algorithm
 - Willing to adhere and undergo all study visits and procedures
 - Able to provide answers to the study questionnaires administered in either English or siSwati
 - Able to provide consent in either English or siSwati
- Exclusion criteria
 - Stated intent to leave Swaziland indefinitely for work or any other reason in the next 6 months (baseline cohort, Cohort A1) or 12 months (post-MC ASI cohort, Cohort A2)

5.3.3 Longer-term Longitudinal cohort (Cohort B)

- Inclusion criteria
 - Completed 12- month follow-up in Cohort A2
 - For males, reported age between 25 – 34 years; for female, reported age between 18 – 24 years
 - Confirmed HIV-negative by Swazi rapid HIV test algorithm
 - Willing to adhere and undergo all study visits and procedures
 - Able to provide answers to the study questionnaires administered in either English or siSwati
 - Able to provide consent in either English or siSwati

- Exclusion criteria
 - Stated intent to leave Swaziland indefinitely for work or any other reason in the next 6 months

5.3.4 Cross-sectional survey (Cohort C)

- Inclusion criteria
 - Completed the pre-cohort A1
 - Confirmed HIV-positive during the pre-cohort A1 by SHIMS testing algorithm
 - Provided written informed consent to be contacted for future research
 - Willing to adhere and undergo all study visits and procedures
 - Able to provide answers to the study questionnaires administered in either English or siSwati
 - Able to provide consent in either English or siSwati
- Exclusion criteria
 - Refused HIV test results during pre-cohort survey
 - Expired consent to be contacted for future research (i.e., more than 12 months have passed since the individual's pre-cohort survey visit occurred)

5.4 Justification for exclusion of sub-segments of the population

Except for the exclusion criteria described above, sub-segments of the population will not be excluded from participation. Persons < 18 years of age will be excluded from study participation, because the age of consent for research participation in Swaziland is 18 years and because HIV incidence in men, the primary population under study, is estimated to increase significantly after 18 years of age. Persons with a stated intention of leaving Swaziland indefinitely may be more easily lost-to-follow-up. Substantial attrition from these persons could reduce the power of the study, and ultimately jeopardize the ability of the study to detect differences in the key study outcomes. During the pre-cohort survey visit, willing participants provided written informed consent to be contact for future research for up to 12 months. For this reason, the cross-sectional survey (Cohort C) excludes participation by those whose consent for future research has expired.

6.0 STUDY PROCEDURES

6.1 Pre-cohort Survey

A size-proportional, representative sample of enumeration areas will be selected. An exhaustive listing of households within each sampled enumeration area will

subsequently occur, and a random sample of households within each enumeration area will be drawn. All eligible persons within sampled households may participate.

6.1.1 Recruitment

Study staff will approach all households included in the sample and make appropriate introductions, provide information about the study, identify the head of household, and ask him or her to identify potentially eligible adults, using the Household Composition Form (Appendix B).

Designated heads of households will be identified and told briefly about the survey as an invitation to learn more. Those who are willing will be asked to provide the age and sex of all usual household members and overnight visitors as well as basic socio-demographic profile of the household. This information will be entered on the Household Composition Form (Appendix B). From this information, household members and those who stayed in the household the previous night who are 18-49 will be identified as eligible to participate.

Those individuals who meet the eligibility criteria will be asked to participate in the pre-cohort survey. Those who decline will be thanked for their time and asked to provide basic information about their reason for declining via the Refusal: Pre-cohort Survey Form (Appendix D) to assist in characterizing the impact of refusal on study outcomes.

Those who agree to participate will be asked to designate a relatively private location either inside or outside their home where the remainder of activities may be conducted with as much privacy as possible, as appropriate. From this chosen area, the participant will be asked to first provide written informed consent for the pre-cohort survey using the procedures described in Section 9.0. See Appendix C.

6.1.2 Enrollment

After providing written informed consent, individuals participating in the pre-cohort survey will receive:

- An interviewer-administered questionnaire that assesses demographic, behavioral characteristics, self-reported MC status and HIV testing history.

Participants who report 2 or more sexual partners in the last 6 months will be asked additional questions regarding multiple and concurrent partnerships.

These questions comprise the Case Report Form: Routine Survey (Appendix E)

- Approximately 500 men and 500 women will be randomly selected to receive a more detailed, extended questionnaire, estimated to take an additional 15-

20 minutes to administer. These questions comprise the Case Report Form: Extended Survey. See Appendix F.

- Standardized pre- and post-test HIV risk reduction counseling and HIV testing using the serial algorithm for rapid HIV testing that is approved for this study (Appendix A).
- Counseling regarding importance of HIV testing for partners and referral to HIV testing sites
- Blood draw of approximately 7-10mL

Once HIV testing is completed in the home, study staff will follow different procedures based on the participant's HIV test result(s). (Note: If after consenting to participate in the survey a participant then refuses the rapid HIV test, then he or she will be re-classified as refusing to participate in the study, and no further study procedures will be conducted. These individuals will be asked to provide basic information about their reason for declining via the Refusal: Pre-cohort Survey Form (Appendix D).)

6.1.2.1 Study procedures for persons who test HIV-positive

- Individuals who test HIV-positive in the home during the pre-cohort surveys will not be eligible to participate in the short-term longitudinal cohorts, Cohort A1 and A2. Likewise, men 25-34 years of age and women 18-24 years of age who test HIV-positive at the follow-up visit for Cohort A2 will not be eligible for enrollment in Cohort B.
- Counseling about the benefits of HIV care and treatment services and information to help such persons link to these services will be provided.
- Counseling regarding the importance of HIV testing of partners and referral to HIV testing sites will be provided.
- Persons who test HIV-positive in the laboratory (following an indeterminate test result in the home) will have their result returned to them in their home within 2 weeks, and the same considerations around cohort eligibility and care and treatment outlined in the three bullet points immediately above will be made.

6.1.2.2 Study procedures for persons who test HIV-negative

- Individuals who test HIV-negative in the home during the pre-cohort surveys will be recruited for participation in the short-term longitudinal cohorts, Cohort A1 and A2. Men 25-34 years of age and women 18-24 years of age who test HIV-negative at the follow-up visit for Cohort A2 will be offered enrollment in Cohort B.
- Persons who test HIV-negative in the laboratory (following an indeterminate test result in the home) will have their result returned to them in their home within 2 weeks, and the same consideration regarding cohort eligibility outlined in the bullet point immediately above will be made.

6.1.2.3 Study procedures for persons with an indeterminate HIV status

- Blood specimens from persons with an indeterminate HIV status according to the results of the rapid tests performed in the home will undergo additional testing at the National Reference Laboratory (Appendix A). The testing algorithm-defined results (Appendix A) from the additional lab test(s) at NRL will determine subsequent activities and timelines:
 - HIV-positive by EIA testing in the lab: Staff will return to the participant's home within approximately two weeks of the initial specimen collection date and inform the participant of his/her HIV-positive test result. Individuals whose blood specimen tests HIV-positive by EIA in the lab and who are not currently enrolled in HIV care and treatment services, will be counseled about the benefits of HIV care and treatment services and provided with information to help them link to these services. Such individuals will also be counseled regarding the importance of HIV testing of partners and referral to HIV testing sites will be provided
 - HIV-negative by EIA/NAT testing in the lab: Staff will return to the participant's home within approximately two weeks of the initial specimen collection date and inform the participant of his/her HIV-negative test result. Individuals whose blood specimen tests HIV-negative in the lab as part of testing during the pre-cohort surveys will be recruited for participation in the short- term longitudinal cohorts, Cohort A1 and A2. Men 25-34 years of age and women 18-24 years of age whose blood specimen tests HIV-negative in the lab at the follow-up visit for Cohort A2 will be offered enrollment in Cohort B.
 - HIV status indeterminate by EIA/NAT testing in the lab: Staff will return to the participant's home within six weeks of the initial specimen collection date and inform the participant of the inconclusive HIV test result. The participant will be encouraged to have blood drawn at that time so that the rapid testing algorithm may be repeated in the home. Results of the repeat, out-of-cycle rapid testing will determine subsequent activities, as outlined in sections 6.1.2.1 – 6.1.2.3 above.
 - Individual participants with indeterminate test results in the lab by EIA/NAT on two separate blood specimens collected 6 weeks apart will be adjudicated on a case-by-case basis.
- A total of 4 attempts over a period of 4 weeks will be made to locate participants to notify them of their HIV status based upon EIA/NAT testing at NRL (and provide repeat HIV testing, if appropriate). If after 4 attempts, the participant is not found, they will be considered lost-to-follow-up.

6.2 Baseline and Post MC ASI Cohorts (A1 and A2)

6.2.1 Recruitment

Participants completing the pre-cohort survey who test HIV-negative will be invited to participate in the baseline or post MC ASI cohorts (A1 or A2). Possible candidates will be provided with a brief description of the cohort study to determine their interest in the study.

Participants who are willing to participate will be asked to provide a separate (different from the pre-cohort survey informed consent) written informed consent using the procedures described Section 9.0. See Appendix H (baseline MC ASI or Cohort A1 ICF) and O (post MC ASI or Cohort A2 ICF).

Eligible men and women who enroll in the baseline cohort (A1) will be followed-up 6 months later. Those who enroll in the post-MC ASI cohort (A2) will be followed-up 12 months later.

Those persons who are eligible but decline enrollment in the cohort will be thanked for their time and asked to provide basic information, using the Refusal: Short Term Cohort Form, to assess reasons for refusal and to assist in characterization of the impact of refusal on study outcomes. See Appendix J.

6.2.2 Enrollment

After providing informed consent for cohort participation, cohort participants will be asked to provide additional locator information to assist with future contact. Telephone numbers, usual hangouts, names of family members/friends who can be contacted for tracing participants with information as to whether the participant agrees to such contact by study staff will be requested. Locator information questions comprise the Locator Information Form. See Appendix I.

6.2.3 Interim Telephone calls

Study staff will attempt to contact cohort participants at 3 month intervals by telephone after enrollment to update locator information and, if needed, approximately two weeks before their scheduled follow-up visit. Cohort participants will be provided with a study telephone number to call for updating their information or for seeking information regarding the study assessments and anticipated scheduled visits. Cohort participants determined to have moved within Swaziland will be visited at their current residence at the time of follow-up assessment (or alternate location of their choice).

6.2.4 Follow-up Visits

Cohort A1 and A2 participants will be visited again at their place of residence for a follow-up visit at 6 months (Cohort A1) or 12 months (Cohort A2) after enrollment.

For each follow-up appointment at the home, at least 3 attempts will be made by study staff to establish contact in person and complete the follow-up visit activities. Visits will

ideally be completed within a specified ± 14 day window around target follow-up dates. The allowable follow-up dates, however, will extend to the date of study conclusion. Detailed information regarding visit windows will be thoroughly described in the SHIMS SOP on retention. The following procedures/assessments are to be performed at the cohort follow-up study visits:

- Verification of the participant's identity and participation in the study
- Selection of a relatively private location either inside or outside the participant's home, so that the follow-up visit may take place with as much privacy as possible, as appropriate review of the study goals and procedures
- For men, an interviewer-administered questionnaire to detect changes in self-reported MC status
- Participants who were uncircumcised at cohort enrollment but circumcised at cohort follow-up will be asked to provide information about the date and location of the MC surgery (Appendix K). Their medical records related to their MC surgery will be abstracted at the facility that performed the MC surgery to determine the date of surgery.
- Blood draw of approximately 7-10mL
 - HIV testing and counseling using the serial algorithm for rapid HIV testing that is approved for this study (Appendix A).
 - See procedures outlined in Section 6.1.2.1-6.1.2.3 for instructions on handling HIV test results.

Those who decline cohort follow-up will be thanked for their time and asked to provide basic information about their reason for refusal to assist in characterizing the impact of refusal on study outcomes. This information will be documented in the appropriate section of the Short/Long-term Cohort Follow-up CRF(s) (Appendices K-N).

6.2.4.1 Additional Study procedures for participants who test HIV-positive at the follow-up visit

- Interviewer administered questions to assess whether the participant has previously tested HIV-positive and whether HIV care and treatment has been sought.
- Counseling about the benefits of HIV care and treatment services and provision of information to help them link to these services.
- Counseling regarding importance of HIV testing of partners and referral to HIV testing sites.
- Male participants identified as newly circumcised **and** newly HIV-infected at follow-up (were uncircumcised at cohort enrollment) will be asked to provide information about the date and location of the MC surgery, whether they had an HIV test the day of the MC surgery, and the HIV test result, to help determine HIV status at the time of circumcision. Their medical records related to their MC surgery will be abstracted at the facility that performed the MC surgery to determine whether an HIV test was conducted pre-operatively and the results of the test, if done.

6.2.5 Cross-Sectional Cohort C

6.2.5.1 Recruitment

A cluster sampled subset of pre-cohort A1 survey participants who test HIV-positive will be invited to participate in the cross-sectional survey (Cross-Sectional Cohort C) at month 0, approximately 6 to 12 months after their initial pre-cohort A1 visit. Only those who consented to be contacted for future research in the pre-cohort A1 Informed Consent Form will be offered participation. Upon first contact with potentially eligible participants, verification of the person's identity and participation in the pre-cohort A1 survey will be conducted according to existing SHIMS SOPs. Procedures will ensure that the potentially eligible participant's HIV-positive status (as determined during the pre-cohort A1 survey) is not revealed until after identity verification.

After identity verification, potential participants will be asked to designate a relatively private location either inside or outside their home. From this chosen area, the potential participant will be provided with a brief description of the cross-sectional survey. Those who agree to participate will be asked to provide written informed consent for the cross-sectional survey using the procedures described in Section 9.0. See Appendix U.

Those persons who are eligible but decline participation in the Cross-Sectional Cohort C sub-study will be thanked for their time and asked to provide basic information, using the Refusal: Cross-Sectional Survey C Form, to assess reasons for refusal and to assist in characterization of the impact of refusal on study outcomes. See Appendix V.

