2.5 Rationale and intended use of study findings

This evaluation will provide important information about changes in HIV incidence over time at a population level, coinciding with the MC ASI program and associated expansion in HIV prevention, care and treatment programs. Also, comparisons of HIV incidence rates among men by circumcision status will better inform our understanding of the reduced risk of acquiring HIV for men who are circumcised in non-research settings. Such information will help refine projections of HIV infections that may be averted and the potential cost savings realized, compared to other prevention and treatment strategies. Results may also demonstrate the effects of newly diagnosing men and women on the proportion of HIV-positive individuals with an undetectable viral load.

Previous statistical studies have modeled CD4 count distribution at a population level (Williams et al, 2006) but no population level measurement has ever been conducted. Population-level measures of the CD4 distribution among HIV-infected and of current ART use among eligible persons would provide nationally representative estimates of ART-eligible persons on ART and in need of ART. As ART-induced viral suppression protects against HIV transmission, an estimate of the number of persons who have a CD4 count less than 350 and who report no current ART use will indicate the proportion of HIV-infected who would benefit from ART both as individuals and at the public health level.

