9.3.2 Potential benefits

Participants will receive several benefits from this study including learning their HIV status. If a participant tests HIV-positive, they will be counseled on the importance of linking to care and treatment; they will also be referred to closest HIV care site. In addition, they will be counseled regarding the importance of partner notification and testing, as well as provided with information regarding HIV testing sites.

For participants who receive CD4 testing, they will have the benefit of knowing this information related to their health status. This information will allow participants to seek care for HIV and to have the benefit of being referred for care and treatment at an earlier stage of illness. Earlier HIV care may offer individual and public health benefits.

Societal benefits of this study include gaining a better understanding of the effectiveness of male circumcision in reducing HIV incidence when provided at a population level in real-world settings. This information will help refine projections of HIV infections that may be averted from MC programs and the potential costs savings realized, compared to HIV care and treatment costs. The study will also contribute to the understanding of whether risk compensation is an unintended consequence of large-scale MC programs.

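### Objective 9 (CD4 below 350 with no current ART) is measured 6 to 12 months after the study's own testing and referral, in a selected subset, yet is presented as a national estimate; it probably understates untreated need, by an unknown amount

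*Protocol*

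**What the plan says.** Protocol Section 5.3.4 restricts Cohort C to people "Confirmed HIV-positive during the pre-cohort A1 by SHIMS testing algorithm". Section 6.2.5.1 places the Cohort C visit "approximately 6 to 12 months after their initial pre-cohort A1 visit".

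At the A1 visit the study acts on a positive result. Section 6.1.2.1 states: "Counseling about the benefits of HIV care and treatment services and information to help such persons link to these services will be provided". Section 9.3.2 adds that "they will also be referred to closest HIV care site".

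Two selection steps follow. Section 5.3.4 lists as an exclusion "Refused HIV test results during pre-cohort survey". Section 6.2.5.1 states: "Only those who consented to be contacted for future research in the pre-cohort A1 Informed Consent Form will be offered participation".

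Current ART use is asked at the Cohort C visit (Section 6.2.5.2), and CD4 is measured only in Cohort C (Section 6.5.1). Section 2.5 says these measures "would provide nationally representative estimates of ART-eligible persons on ART and in need of ART". Section 8.1.4 plans survey-weighted proportions with 95% limits. The non-response weights of Section 7.3 rest on demographic information. The end of Section 7.2 considers non-response and ineligibility only when setting how many people to approach. Neither limitations section (4.4, 8.9) mentions that the A1 visit may alter what Cohort C measures.

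**The concern.** Objective 9 counts people with CD4 below 350 who are not on ART. Anyone who starts ART between the two visits leaves that count. The study has itself given these people a test, a result, counselling and a referral, so some of those starts may be its own doing. The general HIV-infected population had no such visit.

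The protocol accepts this kind of mechanism elsewhere. Section 4.4 names repeated counselling and interviews as a validity threat for the incidence cohorts, and Sections 2.2 and 2.3 expect new diagnosis to lead to linkage and treatment. It does not apply the idea to Cohort C.

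People who declined their results may be less linked to care than those who accepted them. Leaving them out would then lower measured need as well.

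At stake is a planning figure. Sections 2.2 and 2.5 intend these data to show how many eligible people are untreated and whether testing-to-care links need strengthening, and the A1 visit may change exactly that.

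**Working it through.** **Inputs from the protocol (Section 7.2 unless noted).** Half of HIV-infected adults have CD4 of 350 or below, and 40% of eligible adults are not on ART, so expected need is 0.50 × 0.40 = 20%. N = 1,000; design effect at most 3. Men: incidence 2.0 per 100 person-years, 77% uninfected. Women: 3.0 per 100 person-years, 65% uninfected. Section 2.2 projects up to 34,000 men newly diagnosed through the circumcision programme, with 4,500 of those with CD4 below 350 starting treatment.

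**Not given, so assumed below:** the share of untreated eligible people newly diagnosed by the study, the share starting ART because of its visit, and the share refusing results.

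**1. The plan's precision.** Half-width = 1.96 × √(0.20 × 0.80 × 3 / 1,000) = 4.29 points, against 4.30 stated. It reproduces, and covers sampling error only.

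**2. Study-induced ART starts.** Observed need = 20% × (1 − s), where s is the share of untreated eligible people who start ART because of the A1 visit.
- s = 10%: 18%
- s = 30%: 14%
- The shift equals the half-width when s = 4.3 / 20 = 21.5%.

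If only people newly diagnosed by the study respond, s = d × a, with d the newly diagnosed share and a the share of those starting ART. For d from 25% to 100% and a from 10% to 40% (all assumed):
- smallest shift: 20 × 0.25 × 0.10 = 0.5 points (19.5% observed)
- largest shift: 20 × 1.00 × 0.40 = 8.0 points (12.0% observed)

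Borrowing the circumcision-programme projection, and assuming half of those men have CD4 below 350, a = 4,500 / (34,000 × 0.50) = 26.5%. The shift is then 20 × 0.25 × 0.265 = 1.3 points up to 20 × 1.00 × 0.265 = 5.3 points. That projection concerns a different programme and men only, so it is a guide and not an input.

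**3. Result-refusers.** True need = (1 − r) × 20% + r × u, with r the refusing share and u the untreated eligible share among refusers. For r from 1% to 10% and u from 20% to 50% (assumed), true need runs from 20.0% to 0.90 × 20 + 0.10 × 50 = 23.0%, against 20% observed. The shift is 0 to 3 points.

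**4. Infections after A1, opposite direction.** People infected since the A1 visit cannot be in Cohort C. Their share of the infected is i·n·t / (i·n·t + 1 − n), with i incidence, n the uninfected proportion and t years.
- Men, 6 months: 0.0077 / 0.2377 = 3.2%; 12 months: 0.0154 / 0.2454 = 6.3%
- Women, 6 months: 0.00975 / 0.35975 = 2.7%; 12 months: 0.0195 / 0.3695 = 5.3%

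If none of them has CD4 below 350 (assumed), contemporaneous need is 20 × (1 − 0.027) = 19.5% down to 20 × (1 − 0.063) = 18.7%. A 20% estimate would then be too high by about 0.5 to 1.3 points.

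**5. CD4 decline.** Untreated people may fall below 350 between the visits, which raises the measured share relative to the A1 date. The protocol gives nothing to size this.

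**The case against.** The strongest reply is that direction is not demonstrable. No linkage rate, newly diagnosed share or refusal share is given, and steps 4 and 5 push upward. This stands.

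The low testing figures in Section 2.1 (17% of men and 36% of women ever tested with results received) might suggest that most members were newly diagnosed. They come from an older survey of all adults aged 15-49, not of HIV-infected adults at A1. The same section gives modelled ART coverage, at the 350 threshold, of 59% in 2009 and 79.5% in a 2011 report. Many members may have known their status and been only re-tested. Some ART starts would also have happened without the study, given national scale-up and the revised threshold; these are real changes in need, not artefact. Both points stand and limit the size.

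A reader might infer that the study's viral load and ART results are biased generally. They are not: viral load is tested on HIV-positive people at the pre-cohort visit (Sections 6.5.1, 6.7.2), and care and ART use are self-reported then (Sections 6.5.2, 6.5.3). Secondary Objectives 5 and 6 use those data and escape this mechanism.

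It may also be said that Objective 9 asks about current ART use without dating it to A1, and that breakdowns and weighting variables belong in an analysis plan. That is fair for the details. But the protocol itself fixes the timing, the exclusions and the claim of national representativeness, and no analysis plan can make that claim accurate as worded.

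**Conclusion.** The point holds as a probable downward bias, unacknowledged and of unknown size, in Objective 9 and in the concurrent CD4/viral load part of Objective 8. If 10% to 30% of untreated eligible people start ART because of the A1 visit, an expected 20% reads as 18% to 14%; above about 21.5% the bias exceeds the stated half-width. Excluding refusers could add 0 to 3 points in the same direction. Missing recent infections offsets about 0.5 to 1.3 points, and CD4 decline offsets an unknown amount. All linkage and refusal shares are assumptions.

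Three stronger readings are not supported: that the estimate is shown to understate need, that it can be called a lower bound, and that every Cohort C member was diagnosed by the study. The first two fail because of the opposing effects, the third because people who already knew their status were only re-tested.

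**What to change.** 1. Report Objective 9 with ART status at the Cohort C visit and, as a sensitivity analysis, with ART status as of the A1 visit (A1 questionnaire, plus clinic card where available). Show people who started ART in between counted both as CD4 below 350 and as not.
2. Report Objective 9 and the CD4 and viral load distributions separately for people who already knew their status at A1 and for those newly diagnosed by the study.
3. Add A1 ART use, prior knowledge of status and A1 viral load to the Cohort C non-response weights, so that HIV-positive A1 participants excluded for refusing results or lacking future-contact consent are represented.
4. Keep the Objective 8 viral load from the Cohort C specimen, since an A1 value would no longer be concurrent with CD4, and compare it with the same people's A1 viral load.
5. Describe the Cohort C visit estimate as applying 6 to 12 months after home testing and referral, state the limitation, and do not label it a lower bound.

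The cost is some extra analysis and changed wording; no new visits or tests are needed. The drawbacks are that ART history is partly self-reported, clinic cards are not always available, CD4 at Cohort C may already reflect interim ART, and the answer becomes a range.
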